2.2.2 Secondary Endpoints

- Time (hours) from start of labor/IOL to delivery

- Time (hours) from study drug administration to delivery
- Time (hours) from start of second stage of labor to delivery
- Indication for CD
- Operative vaginal delivery
- Cumulative and maximum dose of intrapartum oxytocin received
- Postpartum hemorrhage
- Maternal blood transfusion
- Endometritis
- Chorioamnionitis
- Wound infection
- Other composite maternal morbidity: VTE, Hysterectomy, ICU admission, Maternal readmission within 7 days and 4 weeks, Maternal death
- ICN adm > 48 hours
- Composite neonatal outcome: neonatal blood transfusion, HIE, IVH grade 3 or 4, head cooling, severe RDS, NEC, Sepsis, Death

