3.1 Inclusion Criteria

English-speaking

≥ 16 years of age

≥ 36 weeks gestation

Singleton pregnancy

Vertex presentation

No contraindication to a vaginal delivery

Meets at least one study criteria for prolonged labor:

1. cervical dilation <6 cm after ≥12 hours with ruptured membranes and receiving oxytocin

OR

2. cervical dilation >6 cm and <1 cm dilation change over ≥2 hours with ruptured membranes and receiving oxytocin

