4.3 Concomitant Medications/Treatments

All participants will be already receiving oxytocin for labor augmentation prior to receiving the study medication. No additional labor augmentation agents will be utilized. No additional β -blocker, antihypertensive, or vasoactive medications will be utilized in conjunction with the study medication.

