5.3 Procedures During Treatment

After study enrollment, the covering clinician will place an EPIC order for "investigational study drug" and will retrieve the next available pre-randomized study medication bag that will be available in the labor floor medication room. The number labeling the study medication bag will be recorded by the clinician and the patient's identification label will be applied to the used vial of study medication after administration and returned to IDS for confirmation and record keeping. The time of administration of the study drug will be recorded by the patient's nurse in EPIC. For a repeat dose of medication, the RN will use the second vial of medication

included in the same study medication packet, record the administration of the dose in EPIC, and label and return the medication to IDS in the same manner.

Patients in both groups will undergo similar vital sign monitoring before and after each dose of study medication. Patients will have routine vital sign monitoring every 15-30 minutes depending on the stage of labor (including heart rate, blood pressure, and oxygen saturation assessment) through the duration of their enrollment in the study.

The remainder of clinical care in labor and delivery will occur as per primary OB provider's discretion as described in section 3.4.

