8.1 Sample Size and Accrual

The sample size is based on the expected CD rate for women experiencing prolonged labor of approximately 45%. For a power of 80% and an alpha of 0.05, 326 women would be needed to find a decrease in rate of CD to 30%.

We estimate 40 eligible women deliver at HUP per month. We anticipate approaching 80% of these women or approximately 32 per month. With an estimated 50% consent rate, we would enroll approximately 16 women per month. Therefore, we would need 24 months to reach our target enrollment of 326 women.

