8.2 Data Analyses Plans

Measures of relative risk will include 95% confidence intervals. Descriptive statistics will be presented as mean with standard deviation, median with interquartile range, or proportion with 95% confidence interval based on data type and distribution. Comparisons between groups will be performed using a Chi-square or Fisher's exact test for categorical variables and parametric or non-parametric tests for continuous variables, as appropriate. Intention-to-treat analyses will be conducted such that all patients with available follow-up measures will be included in the analysis. Statistical analyses were conducted in STATA, version 15.1 (College Station, Texas). Two-tailed P values of <0.05 will be considered statistically significant.

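### The secondary oxytocin endpoint includes oxytocin given before the study drug, which treatment cannot change: a likely precision cost for the total and attenuation of the maximum

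*Combined protocol and SAP*

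**What the plan says.** Section 2.2.2 defines the endpoint only as "Cumulative and maximum dose of intrapartum oxytocin received". It states no start, stop or baseline. The word *intrapartum* implies that counting ends at delivery by either route, but this is not written.

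Section 4.3 states: "All participants will be already receiving oxytocin for labor augmentation prior to receiving the study medication". Both prolonged-labor criteria in Section 3.1 also require oxytocin: "cervical dilation <6 cm after ≥12 hours with ruptured membranes and receiving oxytocin", or "cervical dilation >6 cm and <1 cm dilation change over ≥2 hours with ruptured membranes and receiving oxytocin".

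For the analysis, Section 8.2 offers "parametric or non-parametric tests for continuous variables, as appropriate", and the Study Summary names a two-sample t-test. Neither mentions a baseline covariate, the entry criterion or mode of delivery.

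The list in Section 2.2.2 does anchor one other endpoint at the study drug: "Time (hours) from study drug administration to delivery". Section 5.3 secures the timestamp: "The time of administration of the study drug will be recorded by the patient's nurse in EPIC".

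**The concern.** Read literally, the endpoint adds two quantities: oxytocin given before the study drug, which treatment cannot alter, and oxytocin given afterwards, which it might. The two entry criteria admit women with different labor histories, so the first quantity may vary widely for reasons unrelated to treatment. An unadjusted comparison carries all of that variation.

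The maximum has a further problem. If the highest dose was reached before the study drug, later oxytocin sparing cannot lower the recorded value.

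At stake is whether this endpoint can show an effect on oxytocin requirement if there is one, and whether a null result would be informative.

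**Working it through.** **1. The plan's own figure.** Section 8.1 gives 45% versus 30% cesarean, 80% power and alpha 0.05; Section 8.2 makes tests two-tailed. With 1:1 allocation (assumed, not stated) and no continuity correction, mean proportion 0.375:

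n per arm = [1.960 × √(2 × 0.375 × 0.625) + 0.8416 × √(0.45 × 0.55 + 0.30 × 0.70)]² / 0.15² = (1.3419 + 0.5693)² / 0.0225 = 162.3, so 163 per arm and 326 in total.

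This matches the plan and does not depend on the oxytocin endpoint, for which no power figure is given.

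**2. Cumulative dose: bias.** Write total T = A + B, with A the pre-drug and B the post-drug dose. A is fixed before treatment acts, so randomization gives it the same expectation in both arms. The expected arm difference in T therefore equals that in B, and there is no bias.

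**3. Cumulative dose: precision.** Let r = Var(A)/Var(B) and ρ = corr(A, B). Then Var(T) = Var(B) × (1 + r + 2ρ√r). Neither r nor ρ is in the documents, so what follows is illustration. Take the post-drug effect that has 80% power with 163 per arm: (1.960 + 0.842) × √(2/163) = 0.31 SD of B. Power on T is approximately Φ(2.802/√(1 + r + 2ρ√r) − 1.960):

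| ρ | r = 0.25 | 0.5 | 1 | 2 | 4 |
|---|---|---|---|---|---|
| −0.3 | 82% | 77% | 66% | 48% | 30% |
| 0 | 71% | 63% | 51% | 37% | 24% |
| +0.3 | 61% | 52% | 41% | 30% | 20% |
| +0.6 | 54% | 45% | 35% | 25% | 18% |

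Power falls in every cell but one. At r = 0.25 and ρ = −0.3 the variance factor is 1 + 0.25 − 0.30 = 0.95 and nothing is lost.

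**4. Maximum dose.** Let a be a woman's pre-drug peak, and b₁ and b₀ her post-drug peaks under propranolol and placebo. The endpoint records max(a, b). Since |max(a, b₁) − max(a, b₀)| ≤ |b₁ − b₀|, including the pre-drug period can only shrink her contrast, and it becomes zero when a is at least as large as both. If a share q of women are in that position and the rest would all shift by δ, the mean difference is at most (1 − q)δ: 0.75δ at q = 0.25 and 0.5δ at q = 0.5. These values of q are assumptions.

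**5. Pre-drug share of the total.** At a constant rate (assumption) the share is hours before / (hours before + hours after). With 2 h before and 9 to 3 h after: 2/11 = 18% to 2/5 = 40%. With 12 h before: 12/21 = 57% to 12/15 = 80%. The 12 h case applies only if the 12 hours in the first criterion refer to oxytocin as well as to ruptured membranes. A share of the total is also not a share of the variance.

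**6. Mode of delivery.** If mean post-drug oxytocin time differs by D hours between cesarean and vaginal births, the design rates alone move the arm means apart by (0.45 − 0.30) × D = 0.15D. For an assumed D of 2 to 4 h in either direction, that is 0.3 to 0.6 h. With an assumed SD of 3 to 5 h, the standard error is SD × √(2/163) = 0.33 to 0.55 h, and the chance of significance from this route alone is about 8% to 44%. Neither the size nor the sign of D is in the documents.

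**The case against.** The strongest defense is that a whole-labor total is a legitimate descriptive quantity. Section 2.2.2 treats time the same way, listing one duration from the start of labor or induction beside one from the study drug. Randomization balances pre-drug oxytocin in expectation, and this is one line among 14 secondary endpoints.

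Most of that stands. For the cumulative dose the test remains valid: there is no bias and no inflation of type I error. Variation by entry criterion is baseline variation, not confounding. But the defense does not answer the loss of precision, and for the maximum it does not answer the attenuation, which balance between arms cannot undo. Time has a study-drug-anchored counterpart in the list; oxytocin has none.

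Three stronger readings are tempting, and the documents do not support them.

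- *The endpoint is mostly noise.* That needs pre-drug variance to exceed post-drug variance, and no oxytocin SD, rate or duration is given.
- *The endpoint is a proxy for mode of delivery and therefore invalid.* If propranolol changes oxytocin exposure by preventing cesareans, that is a genuine total effect, which the intention-to-treat comparison estimates validly. The issue is interpretation, and the direction of any shift is unknown.
- *Every woman entering under the first criterion has had at least 12 hours of oxytocin.* The 12 hours may qualify ruptured membranes only. That some oxytocin preceded the study drug in every woman rests on Section 4.3, not on this.

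**Conclusion.** The point holds as a minor gap in definition and analysis. As written, both oxytocin measures include exposure that treatment cannot change, and no other section supplies a study-drug anchor or a baseline adjustment. The cumulative dose probably loses precision. The maximum is attenuated to the extent that peaks came before the study drug. The cumulative-dose difference is not biased.

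The loss cannot be sized from the documents; the power table and the values of q show only how it depends on unknown quantities. I read the maximum as the highest infusion rate, which the plan does not spell out. The primary analysis and N = 326 are untouched.

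**What to change.** Define both measures from first study-drug administration to delivery. For women randomized but not dosed, start the window at randomization so that the intention-to-treat comparison keeps them. State whether the maximum means infusion rate.

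Compare arms adjusting for pre-dose oxytocin at the same time origin (infusion rate or cumulative dose) and for entry criterion. In a linear model with pre-dose cumulative dose as covariate, the arm coefficient is the same for the whole-labor total as for the post-dose amount, so adjustment does the work for the cumulative measure. For the maximum, the new window is essential.

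Report the whole-labor total, and results by mode of delivery, as description only. Note that a difference in cumulative dose may partly reflect a change in mode or timing of delivery. The new window does not remove that dependence, and neither would dividing by hours to delivery. Settle the definition before unblinding, so that the window is not chosen after seeing results.

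The cost is small. The whole-labor total is no longer formally tested. The administration time is already recorded, but the infusion rate at that time must be extracted from the chart; the documents do not say that it is captured, although a cumulative dose can hardly be computed without infusion data. An allocation time is also needed for any woman not dosed.

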3 PATIENT ELIGIBILITY

Subjects must meet all of the inclusion and exclusion criteria to be enrolled to the study. Study treatment may not begin until a subject is consented and randomized.

3.1 Inclusion Criteria

English-speaking

≥ 16 years of age

≥ 36 weeks gestation

Singleton pregnancy

Vertex presentation

No contraindication to a vaginal delivery

Meets at least one study criteria for prolonged labor:

1. cervical dilation <6 cm after ≥12 hours with ruptured membranes and receiving oxytocin

OR

2. cervical dilation >6 cm and <1 cm dilation change over ≥2 hours with ruptured membranes and receiving oxytocin

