Propranolol Rescue of Prolonged Labor (PROPEL)

A randomized, double-blind, placebo-controlled multicenter investigation of propranolol's effect on cesarean delivery rate among women with prolonged labor

Principal Investigator: [name], MSCE

Assistant Professor

Division of Maternal Fetal Medicine

Department of Obstetrics and Gynecology

[name]

[name]

[name]

Sub-Investigator(s): [name]

Clinical Fellow

Division of Maternal Fetal Medicine

[figure not shown]
Department of Obstetrics and Gynecology

Study Drug/Study Device: Propranolol hydrochloride

LIST OF ABBREVIATIONS

AE	Adverse event
DSMB	Data safety monitoring board
CD	Cesarean delivery
EFM	Electronic fetal monitoring
GBS	Group B streptococcus
HIE	Hypoxic ischemic encephalopathy
ICN	Intensive care nursery
ICU	Intensive care unit
IDS	Investigational drug service
IOL	Induction of labor
IRB	Investigational review board
IV	Intravenous
IVH	Intraventricular hemorrhage
NEC	Necrotizing enterocolitis
OB	Obstetric
RDS	Respiratory distress syndrome
SAE	Serious adverse event
VTE	Venous thromboembolism

STUDY SCHEMA

Study Summary

Title	Propranolol rescue of prolonged labor
Short Title	PROPEL
Methodology	Double-blind randomized controlled trial
Study duration	24 Months
Study Center (s)	Multi-center: Hospital of the University of Pennsylvania and Pennsylvania Hospital
Objective	To compare cesarean delivery (CD) rates in women given IV propranolol versus placebo for treatment of prolonged labor.
Number of Subjects	326
Diagnosis and Main Inclusion Criteria	
Meets criteria for prolonged labor:
 
 1. cervical dilation <6 cm after \geq12 hours with ruptured membranes and receiving oxytocin OR 2. cervical dilation >6 cm and <1 cm dilation change over \geq2 hours with ruptured membranes and receiving oxytocin 
AND
 
\geq16 years old, \geq 36 weeks gestation; Singleton gestation in vertex presentation; non anomalous fetus

Study Product (s), Dose, Route, Regimen	
IV Propranolol – 2mg; one possible repeat dose \geq2 hours later
 
Normal saline placebo- 2 mL; one possible repeat dose \geq2 hours later

Duration of administration	Eligible for maximum of one repeat dose \geq 2 hours after first until reaches 10cm dilation
Primary Outcome	Cesarean delivery
Statistical methodology	Intention to treat analysis, chi-square test for categorical variables, two-sample t-test for continuous variables

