4 TREATMENT ARMS

4.1 Treatment Dosage and Administration

- Propranolol hydrochloride 2mg IV
 - One possible repeat dose of 2mg IV given ≥ 2 hours later if < 2 cm cervical dilation change over > 2 hours on subsequent exam
- Placebo – 2mL of 1% normal saline solution IV
 - One possible repeat dose of 2mL IV given ≥ 2 hours later if < 2 cm cervical dilation change over > 2 hours on subsequent exam

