4.4 Duration of Therapy

All participants are eligible for a maximum of one repeat dose of the study medication, until they reach 10cm dilation or decision is made to proceed with cesarean delivery, whichever comes first. After this point, they will not be eligible for any further study medication.

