9.5 Adherence to the Protocol

Except for an emergency situation in which proper care for the protection, safety, and well-being of the study patient requires alternative treatment, the study shall be conducted exactly as described in the approved protocol.

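### Women whose labor stalls at exactly 6 cm meet neither prolonged-labor criterion, and no reason is given for leaving them out

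*Combined protocol and SAP*

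**What the plan says.** Section 3.1 lists two definitions of prolonged labor under the lead-in "Meets at least one study criteria for prolonged labor". The first is "cervical dilation <6 cm after ≥12 hours with ruptured membranes and receiving oxytocin". The second is "cervical dilation >6 cm and <1 cm dilation change over ≥2 hours with ruptured membranes and receiving oxytocin". The Study Summary gives the same pair, again with "cervical dilation >6 cm and <1 cm dilation change over" for the second. Section 3 makes every eligibility criterion mandatory.

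Four other places bear on the point:

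- Section 4.1 allows one repeat dose at least 2 hours after the first "if < 2 cm cervical dilation change over > 2 hours on subsequent exam". It sets no dilation bound of its own.
- Section 4.4 permits study drug "until they reach 10cm dilation or decision is made to proceed with cesarean delivery", whichever comes first.
- Section 8.1 bases accrual on a single figure, "We estimate 40 eligible women deliver at HUP per month", with no breakdown by dilation.
- Section 9.5 says that, emergencies aside, "the study shall be conducted exactly as described in the approved protocol".

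**The concern.** The two definitions appear meant to divide labor at 6 cm, with a duration rule below the threshold and a rate-of-change rule above it. Because neither includes the threshold, a woman who has been at 6 cm for two hours or more, on oxytocin with ruptured membranes, fails both.

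Aim 1 concerns women with prolonged labor and makes no exception for arrest at 6 cm, so the trial's result would be applied to women it did not enroll. There is also a practical risk. If some clinicians at the two hospitals apply the text literally and others read the second bound as including 6 cm, screening will be inconsistent, and each enrollment at 6 cm will be a departure from the protocol.

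**Working it through.** **The plan's own figure.** Inputs from sections 8.1 and 8.2: cesarean rates of 45% and 30%, 80% power, two-sided alpha 0.05. Equal allocation is assumed, because the ratio is not stated. With the pooled-variance formula and no continuity correction, and mean rate (0.45 + 0.30)/2 = 0.375:

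n per arm = [1.960 × √(2 × 0.375 × 0.625) + 0.842 × √(0.45 × 0.55 + 0.30 × 0.70)]² / (0.15)² = 162.3, rounded up to 163.

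The total is 326, as stated. No input depends on the 6 cm bound.

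**The eligibility rule.** Take a woman with no change over 4 hours, and 14 hours with ruptured membranes on oxytocin. Only her dilation varies.

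| Dilation (cm) | As written | With ≥6 cm in criterion 2 |
|---|---|---|
| 5 | eligible | eligible |
| 5.5 | eligible | eligible |
| 6 | **not eligible** | eligible |
| 6.5 | eligible | eligible |
| 7 | eligible | eligible |

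The change alters the result at 6 cm and at no other value tested.

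**Is it a reading error in the text?** Probably not. The strict sign before 6 cm appears in both the Study Summary and section 3.1, and in both places the ≥ sign before 2 hours survives in the same criterion.

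**Is 6 cm treated as unsuitable elsewhere?** No. A participant enrolled at 5 cm who is found at 6 cm after more than 2 hours has changed by 6 − 5 = 1 cm. That is less than 2 cm, so section 4.1 allows the repeat dose at 6 cm. None of the exclusions in section 3.2 mentions 6 cm.

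**Accrual.** From section 8.1: 40 eligible per month × 0.80 approached × 0.50 consenting = 16 per month, and 326/16 = 20.4 months (the plan allows 24). Let s be the share of candidates who are at exactly 6 cm. The documents do not give it, so s = 5% to 20% is an assumption.

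*If the 40 per month already include these women:*

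| s | Lost per month (16 × s) | Enrolled per month | Months to 326 |
|---|---|---|---|
| 5% | 0.8 | 15.2 | 326/15.2 = 21.4 |
| 20% | 3.2 | 12.8 | 326/12.8 = 25.5 |

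Finishing in 24 months needs 326/24 = 13.58 per month, so the plan is exceeded only when s is above 1 − 13.58/16 = 15.1%.

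*If the 40 exclude them:* planned accrual is unaffected. The rule forgoes 16 × s/(1 − s) women per month, which is 0.8 at 5% and 4.0 at 20%.

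**The case against.** The strongest reply is that this is a small matter of boundary wording. Several parts of that reply stand:

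- **The affected group is narrower than everyone seen at 6 cm.** A woman still below 6 cm at 12 hours could have qualified before reaching 6 cm, and one who moves past 6 cm and stalls again can qualify later. Those with no opportunity are mainly women who reach 6 cm before 12 hours and go no further.
- **The accrual effect is uncertain.** The share is assumed. Taken literally, the section 8.1 count of eligible women leaves out those at 6 cm, and then the forecast is untouched. That count also covers only one of the two hospitals, so any recruitment at the second would shorten every duration above.
- **Section 9.5 is not the whole text.** Section 9.5.2 allows planned deviations with prior approval from the principal investigator and the IRB.
- **The repeat-dose argument is limited.** Section 4.1 applies to women already enrolled and uses a different progress test. It shows that 6 cm is not treated as unsafe for dosing; it does not show how entry was meant to be defined.

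None of this closes the gap. A woman who reaches 6 cm early and stays there has arrest of labor, never qualifies, and cannot reach full dilation, so her labor would be expected to end in the primary outcome. A case-by-case deviation is a poor substitute for a correct criterion.

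**Conclusion.** The concern holds. As written, a woman at exactly 6 cm is ineligible while she remains there, and nothing in the documents explains or supports this. The consequence is for representation, for consistent screening, and possibly for accrual. Eligibility is settled before allocation, so the comparison between arms is not biased, and N remains 326.

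The logical gap needs no assumption. Its size does: the accrual range rests on an assumed 5 to 20% share, on whether the forecast counted these women, and on recruitment at one hospital only. The rule should be corrected, but it does not threaten the validity of the trial.

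**What to change.** In the Study Summary and section 3.1, change the second criterion to dilation ≥6 cm, keeping less than 1 cm of change over at least 2 hours, ruptured membranes and oxytocin. As an optional alignment with the dosing limit in section 4.4, add an upper bound of <10 cm. If the omission was deliberate, the protocol should give the reason.

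The cost is a one-line amendment in two places. It widens the eligible pool slightly, adds no procedure and leaves N unchanged.

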3.2 Exclusion Criteria

Severe preeclampsia: as patients will be receiving magnesium and possibly labetalol for hypertension control

Receiving other beta blocker

Maternal heart rate < 70 beats per minute, systolic blood pressure <90 mmHg, or diastolic blood pressure <50 mmHg on two sets of vital signs in the 1 hour prior to study drug administration: given that bradycardia and hypotension are possible side effects of propranolol

History of any form of asthma: as this is a contraindication to beta blocker use

Diabetes requiring insulin in labor: given the potential risk of neonatal hypoglycemia in the neonate

Any cardiac condition for which β blockade is contraindicated (cardiogenic shock, sinus bradycardia, and greater than first degree heart block)

Known hypersensitivity to propranolol

Intrauterine fetal demise since different labor protocols are used in these women

Major fetal congenital anomaly since rate of cesarean may be inherently different in these women, unrelated to labor

